#### **5.3.3 Mixed Meal Challenge: day of participant's choice between Days 3 and 9**

- Participant wears CGM, ActiGraph continuously
- After minimum 10 hours of fasting overnight, participant eats food item of their choice that contains at least 50 grams carbohydrate as well as fat and protein, without any additional food or drink, and remains as inactive as possible for 2 hours
- Text messages sent 3 times daily (10 AM, 2 PM, 8 PM) to collect nutrition, physical activity, sleep records

- At next available survey time, participant indicates time that mixed meal challenge was completed, as well as food item chosen and nutritional content (amount, and carbohydrates, fat, protein per serving)

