**Statistical And Analytic Plan**

Demographic and clinical characteristics will be described using summary statistics, including means, standard deviations, medians, and ranges for continuous variables, and frequencies for categorical variables. Analyses will be conducted using Stata 17 (StataCorp, College Station, TX). Raw actigraphy data will be processed using GGIR, a package in R: A language and environment for statistical computing (R Corp Team, Vienna, Austria). The significance level for two-sided hypothesis testing will be set at 0.05.

To assess completeness of CGM data, the number of days with adequate CGM data will be divided by 9, omitting the first 24 hours due to possible inconsistent measurements after initial placement. Feasibility will be defined as  $\geq 80\%$  (7.2) of days with data. To assess completeness of glucose and mixed-meal challenge documentation, the number of participants who document the date and time of glucose and mixed-meal ingestion (including mixed-meal content) will be determined and divided by the total number of participants (40). Feasibility will be defined as  $\geq 80\%$  of participants documenting date and time of either the glucose challenge, mixed-meal challenge, or both. To evaluate test performance characteristics, sensitivity, specificity, and positive and negative predictive values of glucose on CGM 2 hours after at-home glucose beverage ingestion (CGM-2h) to predict OGTT-2h $\geq 140$  mg/dL will be assessed for various thresholds of CGM-2h. Area under the receiver operating characteristic curve (AUC) will be determined. An AUC threshold of  $\geq 0.7$  will be used to define adequate discrimination. Acceptability will be rated on a Likert scale (1: completely unacceptable, 2: mostly unacceptable, 3: neutral, 4: mostly acceptable, 5: completely acceptable). Acceptability will be defined as a mean score for all participants of  $\geq 3$ . Interview transcripts will be reviewed by study staff trained in qualitative analysis. Content analysis will be used to identify themes and sub-themes.

---

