#### **5.3.2 Glucose Challenge: day of participant's choice between Days 3 and 9**

- Participant wears CGM, ActiGraph continuously
- After minimum 10 hours of fasting overnight, participant drinks study-provided glucose beverage without any additional food or drink and remains as inactive as possible for 2 hours
- Text messages sent 3 times daily (10 AM, 2 PM, 8 PM) to collect nutrition, physical activity, sleep records
  - At next available survey time, participant indicates time that glucose beverage was consumed (start and finish times)

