### 7.4 Statistical Methods

#### 7.4.1 Analysis of Primary and Secondary Outcomes of Interest

Primary objective: Determine the feasibility of at-home, CGM-based glycemia evaluation as measured by adequacy of CGM data capture and nutrition logging quality and completion on days of at-home glucose and mixed-meal challenge.

*H1a: Complete CGM data will be available for  $\geq 80\%$  of requested days worn:* The number of days with adequate CGM data will be divided by 9, omitting the first 24 hours due to possible inconsistent measurements after initial placement. Feasibility will be defined as  $\geq 80\%$  (7.2) of days with data.

*H1b: Documentation of glucose and mixed-meal challenge will be complete and adequate for analysis for  $\geq 80\%$  of participants:* The number of participants who document the date and time of glucose and mixed-meal ingestion (including mixed-meal content) will be determined and divided by the total number of participants. Feasibility will be defined as  $\geq 80\%$  of participants documenting date and time of either the glucose challenge, mixed-meal challenge, or both.

Secondary objective: Determine the test performance characteristics of at-home, CGM-measured glucose challenge with laboratory-based 2-hour OGTT.

*H2: CGM-measured glucose 2 hours and 5 minutes after standardized glucose ingestion will have adequate discrimination of normal ( $<140$  mg/dL) versus dysglycemic ( $\geq 140$  mg/dL) 2-hour OGTT glucose, as assessed by area under the receiver operating characteristic curve  $\geq 0.7$ :* Using participant logs via text message survey or paper-based logs, date and time of home glucose challenge will be determined and labeled in CGM data. A time point 2 hours and 5

---

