minutes later (accounting for lag due to interstitial measurement)(Wadwa, Laffel et al. 2018) (CGM-2h) will serve as the comparison to the 2-hour glucose during OGTT obtained at the study visit (OGTT-2h). Sensitivity, specificity, and positive and negative predictive values of CGM-2h to predict OGTT-2h $\geq$ 140 mg/dL will be assessed for various thresholds of CGM-2h. Area under the receiver operating characteristic curve (AUC) will be determined. An AUC threshold of  $\geq$ 0.7 will be used to define adequate discrimination. The same analysis will be repeated for the comparison of baseline CGM glucose (at time of glucose ingestion) to fasting glucose on OGTT, using a fasting glucose threshold of  $\geq$ 100 mg/dL to define dysglycemia. Finally, correlation analyses (Spearman or Pearson depending on distribution) will be performed to further explore the relationship between CGM indices obtained during at-home glucose challenge (e.g., baseline, peak, mean glucose) and both laboratory-measured HbA1c and plasma glucose during OGTT. Correlations will be examined across subgroups such as lower versus higher ActiGraph-measured physical activity level and self-reported carbohydrate intake on the day prior to at-home glucose challenge, age, pubertal stage, and body mass index.

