#### 7.4.3 Exploratory analyses

The analyses for at-home glucose challenge described above will be repeated to evaluate the test performance of at-home mixed-meal challenge in comparison to 2-hour OGTT. In addition, CGM metrics such as average, area under the curve, and peak glucose as well as coefficient of variation will be compared for days of CGM wear without glucose or mixed-meal challenge versus challenge days to assess the difference in glucose trends of typical daily life versus those artificially imposed by testing.

An additional exploratory analysis will use responses from the disordered eating questionnaire to assess whether correlations between OGTT and CGM-measured glycemia differ between youth with higher versus lower self-report of loss-of-control eating.

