#### 7.4.4 Missing Data

The CGM measures interstitial glucose every 5 minutes, but glucose data may be missing due to signal disruption or mechanical dislodgment. Periods of missing data for more than

20 minutes will not be replaced. For data gaps of up to 20 minutes, the two glucose values preceding and following the missing period will be averaged and used to replace the missing data.

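### The mixed-meal log in 5.3.3 does not clearly collect a start time, so time zero is ambiguous for the exploratory mixed-meal analysis in 7.4.3

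*Combined protocol and SAP*

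**What the plan says.** The two challenges are logged differently.

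- **Glucose beverage (5.3.2):** at the next survey, "participant indicates time that glucose beverage was consumed (start and finish times").
- **Mixed meal (5.3.3):** at the next survey, "participant indicates time that mixed meal challenge was completed, as well as food item chosen and nutritional content". No start time is requested.
- **Synopsis (Study Phases) and 4.1.3:** both tell participants to record when they drank the glucose. Neither gives a matching timing instruction for the meal.

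The statistical text assumes more than 5.3.3 asks for. H1b in 7.4.1 counts participants who "document the date and time of glucose and mixed-meal ingestion (including mixed-meal content"), and the synopsis says the same: "the number of participants who document the date and time of glucose and mixed-meal ingestion (including mixed-meal content) will be determined". Neither says whether the time is the start or the end of intake.

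For the analysis itself, 7.4.3 states: "The analyses for at-home glucose challenge described above will be repeated to evaluate the test performance of at-home mixed-meal challenge". The analyses being repeated use two time points, both tied to ingestion:

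- **Baseline:** "comparison of baseline CGM glucose (at time of glucose ingestion) to fasting glucose on OGTT".
- **Index value:** "CGM-measured glucose 2 hours and 5 minutes after standardized glucose ingestion".

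**The concern.** An analysis anchored on ingestion needs a defined time zero. For the beverage, start and finish are both logged. For the meal, the single time in 5.3.3 can be read in three ways: when the challenge was carried out, when eating ended, or when the 2-hour inactive period ended, since 5.3.3 makes that period part of the challenge. Participants answer afterwards, at the next of three daily surveys, and may not all read the item alike.

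If the time marks the end of eating, the nominal baseline is read after intake has begun and the index value is read later than intended. The delay equals the length of the meal, which is not recorded and differs between participants, so no constant correction removes it. At stake are the exploratory test performance of the mixed meal and any comparison of it with the glucose challenge. A start time that was never asked for cannot be reliably recovered later.

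**Working it through.** **Inputs from the documents**

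- Index point: 2 h 5 min after ingestion, so 120 + 5 = 125 min (7.4.1). The extra 5 minutes allow for interstitial lag.
- CGM interval: "The CGM measures interstitial glucose every 5 minutes" (7.4.4).
- Beverage: drunk over 5 minutes (synopsis, Study Phases). Start and finish therefore differ by 5 / 5 = 1 CGM reading.
- Meal: self-chosen, at least 50 g carbohydrate, after a fast of at least 10 hours, with no limit on eating time (5.3.3).

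**Assumption.** The documents give no meal duration *d*. A range of 5 to 30 minutes is used.

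**If the logged time is the end of eating**

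- Baseline is read *d* minutes after the first bite, which is *d* / 5 readings late.
- The index value is read 125 + *d* minutes after the first bite.

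| Assumed meal (min) | Baseline late by (CGM readings) | Index value, min from first bite |
|---|---|---|
| 5 | 5/5 = 1 | 125 + 5 = 130 |
| 10 | 10/5 = 2 | 125 + 10 = 135 |
| 15 | 15/5 = 3 | 125 + 15 = 140 |
| 20 | 20/5 = 4 | 125 + 20 = 145 |
| 30 | 30/5 = 6 | 125 + 30 = 155 |

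With a logged start time, baseline is at 0 and the index value at 125 minutes whatever the meal length.

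**If the logged time is the end of the rest period**, and the rest starts when eating ends, both points move a further 120 minutes.

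**Effect on the AUC.** In 7.4.1 the cut-offs of 100 and 140 mg/dL define dysglycemia on the laboratory OGTT, which is the reference. CGM is judged at various thresholds and by AUC. The AUC depends only on how participants rank, so a glucose shift common to all leaves it unchanged and merely moves the CGM threshold. Harm comes from the part of the error that differs between participants, which unequal meal lengths produce.

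The plan's one sample-size figure, 40 × (1 − 0.20) = 32 evaluable (7.5), reproduces but does not bear on this point.

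**The case against.** The strongest reply is that the plan does intend to capture an intake time. The synopsis and H1b say so, and the abstract uses *complete* in the sense of carrying out a challenge, so the item in 5.3.3 may simply ask when the meal was eaten. This largely stands. It makes the end-of-rest reading the least likely of the three, and the defect is inconsistent wording, not a decision to omit intake time. It does not settle whether the time is the start or the end of eating.

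Second, a reader might infer that a baseline and a 2-hour value cannot be obtained at all. The documents do not support that. The CGM trace runs through the fast before the meal, so a fasting value can be approximated, and a 2-hour value exists with an error of up to the meal length if the log marks the end of eating. Section 4.1.2 also says that actigraphy will help define eating periods. But the plan sets no look-back rule and no rule for deriving a meal start from actigraphy, and inferring the start from the glucose rise would take the anchor from the signal under test.

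Third, a reader might infer false positives at 100 mg/dL and false negatives at 140 mg/dL. Those cut-offs apply to the laboratory values, not to CGM, so the inference fails.

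Fourth, an error in mg/dL needs outside assumptions. Suppose glucose rises at 1 to 2 mg/dL per minute from 10 minutes after the first bite, with a 5-minute lag. The baseline shift is then max(0, *d* − 10 − 5) × slope: zero for meals of 15 minutes or less, 5 to 10 mg/dL at 20 minutes and 15 to 30 mg/dL at 30 minutes. The example foods in 9.3.2 are snack-sized, so short meals are plausible. A downward bias at 2 hours further assumes that every participant's glucose is falling. No mg/dL figure is relied on here.

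**Conclusion.** Section 5.3.3 is inconsistent with 5.3.2, and it does not clearly supply the ingestion time that the synopsis, H1b and 7.4.3 presuppose. Time zero for the mixed-meal analysis is therefore ambiguous. If the log marks the end of eating, and meals last between 5 and 30 minutes (an assumption), both time points are 1 to 6 CGM readings late and the index value falls at 130 to 155 minutes instead of 125. The values can be approximated but not timed reliably.

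The consequence is added noise in an exploratory AUC and in its comparison with the glucose challenge. A reader might infer that a primary or secondary result is compromised, but the documents do not support that. H2 uses the beverage, whose times are logged. The H1b criterion is met by documenting either challenge or both, so the wording of the meal item can matter only for participants who document the meal alone. The CGM completeness criterion does not use meal times. The point is worth correcting because the remedy is very cheap and the start time cannot be reliably recovered afterwards.

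**What to change.** 1. **5.3.3:** ask for the start and finish times of the meal, in the form already used for the beverage in 5.3.2.
2. **7.4.3:** define time zero for the meal as the start of eating. Take baseline from the last CGM reading at or before it, and the index value 2 h 5 min after it.
3. **7.4.1:** name the same anchor, the start of intake, for the glucose challenge. Two times are logged there but the text does not say which is used, and the two challenges should be timed alike.

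The cost is one extra field in an existing text survey and a sentence each in 7.4.3 and 7.4.1. The added burden on participants is trivial.

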#### **5.3.4 Removal and Return of CGM and ActiGraph: Day 10**

- Midday on the 10th day of CGM wear, participants will remove CGM by painlessly peeling off the adhesive and device
- Sensor and transmitter will be placed in a Ziploc bag and placed in the prepaid, addressed envelope for return
- ActiGraph will be removed from wrist and placed with CGM in envelope
- Envelope will be sent to study team by participant
- Compensation will be provided to participants upon receipt of the CGM and ActiGraph

#### **5.4 Individual Interview and Disordered Eating Questionnaire: any time between Day 10 of Observation Period and 1 month after Study Visit**

- Participants (ages 15-18) or their parents (for participants ages 8-14) will be invited to participate in a 30-minute semi-structured individual interview via phone or videoconferencing platform to assess the acceptability of CGM use as an alternative to clinical OGTT for diabetes risk assessment.
- Participants will be asked to complete a brief, 12-item questionnaire related to disordered eating behaviors in the past 28 days. This will be completed via REDCap. Participants will be allowed to skip questions if they are uncomfortable answering
- Participants will be compensated \$15 for completion of the interview.

#### **5.5 CGM, ActiGraph Data Extraction**

- Dexcom G6 Pro receiver will be used to transfer CGM sensor data to Dexcom Clarity (<https://clarity.dexcom.com/professional/>)
- ActiGraph data will be uploaded from the device using ActiLife software on the PI's UPMC desktop computer

#### **5.6.1 Early Termination Procedures**

Subjects who withdraw from the study will be asked to complete the interview to assess reasons for early termination and will be asked to return the CGM and ActiGraph device via the prepaid envelope. Full compensation will still be provided upon receipt of the devices.

## 6 STUDY EVALUATIONS AND MEASUREMENTS

### 6.1 Screening and Monitoring Evaluations and Measurements

#### 6.1.1 Medical Record Review

Participants will be interviewed regarding their medical history. To ensure that no major items are missed and to clarify interview answers, the study team will review participant electronic medical records prior to and after the participant interview to confirm the following:

- Date of birth
- Birth history (gestational age, birth weight, complications during pregnancy)
- Anthropometrics (weight, height, BMI)
- Medications
- List of medical problems, especially as they relate to inclusion and exclusion criteria
- Demographic data including race, ethnicity, gender, and insurance type
- Endocrine-related diagnoses, including: insulin resistance, prediabetes, impaired glucose tolerance, impaired fasting glucose, elevated hemoglobin A1c, diabetes mellitus, and polycystic ovary syndrome
- History of attendance at an obesity clinic
- History of bariatric surgery
- Diabetes-related labs, including: plasma and point-of-care glucose, hemoglobin A1c, and insulin
- History of non-alcoholic fatty liver disease, non-alcoholic steatohepatitis, elevated ALT or AST, or other known liver disease

#### 6.1.2 Physical Examination

A study physician (pediatric endocrinologist) will review with the parent and child the child's current and past medical history, a review of systems, and family history (with particular attention to cardiovascular disease and diabetes). A focused physical examination will be conducted, including measurement of height, weight, waist circumference, hip circumference, pubertal staging, and pertinent physical findings associated with insulin resistance, including the presence of acanthosis nigricans, which will be recorded on a standardized form. Investigators will verify that the patient has been fasting for a minimum of 10 hours.

---

### 6.1.3 Vital Signs

- Blood pressure (BP) will be recorded while the subject is sitting down by the nursing staff. BP will be measured by auscultation three times, after a five minute rest in a quiet area with the subject in a seated position; the average of the 2nd and 3rd measurements will be used.
- Pulse and respiratory rate will be measured by nursing staff

### 6.1.4 Laboratory Evaluations

#### 6.1.4.1 *Table: Clinical Laboratory Tests*

Category	Tests
Biomarkers of glucose metabolism	Hemoglobin A1c, plasma glucose, insulin, c-peptide

#### 6.1.4.2 Pregnancy Testing

A urine pregnancy test will be performed for all female subjects at baseline. A positive pregnancy result will be disclosed to the participant only. Pregnancy results will be disclosed to the parent/guardian if the subject gives the investigators permission. Subjects found to be pregnant during the visit will not be able to enroll in this study. The investigators will counsel the subject and guide them to seek the appropriate care.

### 6.1.5 Medical History, Family History, Social History Questionnaire

Will include past medical history, 1st and 2nd degree family history of diabetes, dyslipidemia, cardiovascular disease, and socioeconomic status questions. Social history will include questions to understand predictors of acceptability of the intervention, including parent/guardian's employment (hours worked, flexibility of hours), household income, approximate travel time to UPMC Children's Hospital of Pittsburgh from their home, child's school start time, number of missed days of school this year related to medical appointments or assessments, child's school performance (excellent, average, below average, failing), household size (number of adults, number of children), insurance type (commercial/government), and use of government assistance (e.g. SNAP, WIC, public housing).

### 6.1.6 Interview and Disordered Eating Questionnaire

Semi-structured individual interviews will be conducted by study staff after the observation period to evaluate acceptability of use of CGM for diabetes risk assessment, including barriers and facilitators to this approach. Interviews will be audiorecorded and then professionally transcribed for qualitative analysis using NVivo software.

The disordered eating questionnaire includes 12 questions that inquire about the feeling of “loss of control” when eating. This questionnaire does not have a validated threshold for normal versus abnormal and is not in clinical use in its form in this study.

## **6.2 Efficacy Evaluations**

CGM data completeness (data available for  $\geq 80\%$  requested days worn), nutrition logging quality and completion ( $\geq 80\%$  of participants documenting date and time of glucose challenge, mixed meal challenge, or both), and acceptability (mean score  $\geq 3$ , or “neutral” for all participants) will be used to determine feasibility and acceptability of this approach.

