Real-time continuous glucose monitors (CGM) are promising new tools for risk stratification in individuals with dysglycemia. These patient-worn medical devices measure interstitial glucose every 5 minutes and are increasingly used in clinical practice for diabetes management, particularly for type 1 diabetes. This technology offers glimpses into an individual's everyday life, which may include consumption of carbohydrates in amounts larger than that assessed in an OGTT, enhancing test sensitivity. Whether use of CGMs to evaluate type 2 diabetes risk in free-living youth is feasible and acceptable to patients and families is unknown. Assessment of CGM with standardized, but practical, home-based glucose and mixed-meal challenges is needed to determine facilitators and barriers to use of this technology-driven approach in clinical practice. Without advancement in the approach to screening for youth-onset T2D, there is ongoing risk of failure to understand which individuals are at highest risk for complications and could benefit the most from intervention early in the disease process.

The overall objective for this study is to determine whether CGM paired with technology-driven health behavior data collection is a feasible and acceptable approach to T2D screening for youth and their caregivers. The central hypothesis is that CGM, text message-based surveys, and home-based glucose challenge will allow for accurate classification of diabetes risk while providing an acceptable alternative to clinical OGTT for families.

Previous research has demonstrated the strong correlation between several CGM indices and HbA1c or 2-hour glucose on OGTT in youth with obesity and dysglycemia,(Chan, Pyle et al. 2015) and home-based glucose challenge with CGM appears promising for use in adults across the glycemia spectrum.(Dehghani Zahedani, Shariat Torbaghan et al. 2021) Determination of the feasibility and acceptability of CGM with home-based glucose challenge in youth at risk for T2D will pave the way for a new screening method that minimizes family burden while maximizing data quality and ability to accurately risk-stratify.

---

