### **3.1 Primary Objective**

The primary objective is to determine the feasibility of at-home CGM-based glycemia evaluation as measured by adequacy of CGM data capture and nutrition logging quality and completion.

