#### 4.1.3 Observation Period

Participants will be instructed to participate in their typical daily routines, with the exception of two at-home challenges: 1) glucose, and 2) mixed-meal. The ***at-home glucose challenge*** will serve as the primary comparison to the laboratory-measured OGTT. For this challenge, participants will be asked to drink the same glucose solution (Trutol) consumed as part of the OGTT at PCTRCC and provided with the appropriate weight-based amount. They will be instructed to choose a day between days 3 and 9 of the study period during which they will be able to fast for at least 10 hours, drink the glucose beverage, and then be inactive for 2 hours. They will log the date and time of glucose ingestion. For the ***at-home mixed-meal challenge***, participants will be asked to choose a day between study days 3 and 9, separate from the glucose challenge day, during which they will be able to fast for at least 10 hours, eat a snack or meal with at least 50 grams of carbohydrate as well as fat and protein content, and then be inactive for 2 hours. All participants and families will be instructed on determination of carbohydrate content using example foods that they typically consume. Participants will receive \$20 for travel to the study visit, loaded onto a university payment card.

***Text message-based surveys and actigraphy:*** Participants will be sent surveys 3 times daily via text message, inquiring about food and drink intake, physical activity, and time in bed (start/stop times). Survey responses will be collected via Mosio and entered in Research Electronic Data Capture (REDCap), a secure, web-based application for clinical research data collection. Branching logic will be used in REDCap so that participants will only need to provide detail for relevant activities each time. As an incentive for ActiGraph wear, participants will earn an additional \$20 if the ActiGraph device is worn for at least 8/10 days.

***Study completion:*** On day 10 of CGM wear (or earlier in case of discomfort), participants will remove the sensor and transmitter at home by simply peeling off the device. Transmitter and ActiGraph will be returned to the study team by participants using prepaid shipping envelopes or in-person if preferred. Upon receipt of the transmitter and ActiGraph, participants will receive compensation for participation in the study (\$100).

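### The plan contradicts itself on the nutrition-logging criterion: the count includes mixed-meal content, but the rule that decides feasibility needs only a date and time for either challenge

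*Combined protocol and SAP*

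**What the plan says.** **Objective.** Section 3.1 judges feasibility by "adequacy of CGM data capture and nutrition logging quality and completion". Section 7.4.1 restates this with a scope: "nutrition logging quality and completion on days of at-home glucose and mixed-meal challenge". The abstract, the synopsis objective and the primary endpoint in 7.1 are narrower and refer to the at-home glucose challenge only.

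**Count sentence (synopsis and H1b in 7.4.1).** The numerator is "The number of participants who document the date and time of glucose and mixed-meal ingestion (including mixed-meal content"), divided by the total number of participants, which the synopsis gives as 40. The H1b hypothesis also asks that documentation be complete and adequate for analysis. Adequate is not defined.

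**Feasibility sentence (next sentence in both places).** The pass mark is at least 80% "of participants documenting date and time of either the glucose challenge, mixed-meal challenge, or both". Section 6.2 gives this version alone: "of participants documenting date and time of glucose challenge, mixed meal challenge, or both".

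**What is collected.** For the glucose drink, 5.3.2 asks for start and finish times. For the mixed meal, 5.3.3 asks for the time, the food chosen, the amount, and carbohydrate, fat and protein per serving. The general food survey is described in 4.1.3: "Participants will be sent surveys 3 times daily via text message, inquiring about food and drink intake". Paper logbooks are the back-up (4.1.2).

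**The concern.** Between the count sentence and the feasibility sentence two things change. The mixed-meal content disappears, and both challenges become either one. The two sentences cannot both decide H1b, and 6.2 carries only the weaker one.

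An analyst who follows the sentence labelled as the definition could report that logging quality met its bar when no participant had recorded a food item. That would be one of the two primary feasibility conclusions. A reader planning a larger study would take it as evidence that families can log a meal usably by text message, and the rule does not test that.

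The food records also have a later use. Section 7.4.1 examines correlations in subgroups that include "self-reported carbohydrate intake on the day prior to at-home glucose challenge". A pass on the present rule says nothing about whether those entries exist.

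**Working it through.** **1. Reproduce the plan's figures.** The bar is 0.80 × 40 = 32 participants. Section 7.5 expects 40 × (1 − 0.20) = 32 evaluable. Both reproduce. No power or error rate is attached to the feasibility rule; it is a cut-off on an observed proportion.

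**2. Set the two rules side by side.**

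| Log held by a participant | Count sentence (both challenges, with meal content) | Feasibility sentence and 6.2 |
|---|---|---|
| Glucose-drink time only | not counted | success |
| Mixed-meal time only, no food content | not counted | success |
| Both times, no food content | not counted | success |
| Both times, with food content | counted | success |

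The first row carries the point. Section 5.3.2 asks only for times for the glucose drink, so a complete glucose log contains no food information. Thirty-two such participants give 32/40 = 80% and a pass.

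The second row shows that the rule does not match the narrower scope of the abstract and 7.1 either. A participant with no glucose-challenge time is still a success.

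**3. Effect of dropping content.** Assume that 90% of participants log a challenge time. The probability of at least 32 of 40 is P(Bin(40, 0.90) ≥ 32) = 0.985, whatever share of entries has food content. If content is also required and is present for a share c of those participants, the success probability is 0.90 × c:

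| c | 0.90 × c | P(at least 32 of 40) |
|---|---|---|
| 1.00 | 0.90 | 0.985 |
| 0.90 | 0.81 | 0.655 |
| 0.75 | 0.675 | 0.060 |
| 0.50 | 0.45 | 0.000 |

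**4. Effect of either against both.** Assume that each challenge is logged independently with probability p. Either has probability 1 − (1 − p)² and both has p².

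| p | Either | P(pass) | Both | P(pass) |
|---|---|---|---|---|
| 0.60 | 0.84 | 0.82 | 0.36 | 0.00 |
| 0.70 | 0.91 | 0.99 | 0.49 | 0.0001 |
| 0.80 | 0.96 | 1.00 | 0.64 | 0.02 |

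The rates in steps 3 and 4 are assumptions, since the plan gives none. They show that the choice of sentence can reverse the result. They do not predict it.

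**5. How easily would the time rule be met?** This cannot be fixed from the documents. Suppose that each text prompt is answered independently with probability 0.5 and that the glucose challenge can be reported at k prompts. The probability of documentation is 1 − 0.5^k:

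| k | Documented | P(at least 32 of 40) |
|---|---|---|
| 1 | 0.50 | 0.0001 |
| 2 | 0.75 | 0.30 |
| 3 | 0.875 | 0.945 |

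If each participant also has a 20% chance of logging nothing (the 7.5 rate, read as complete non-logging), the k = 3 case becomes 0.80 × 0.875 = 0.70, with pass probability 0.11. The range is too wide to support any claim that the rule is nearly certain to pass.

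**The case against.** **Nutrition data are not absent from the plan.** The count sentence includes mixed-meal content, and H1b asks for documentation adequate for analysis. This stands. A reader might infer from 6.2 alone that the plan never uses nutrition data for this criterion; the synopsis and 7.4.1 do not support that. The fault is a contradiction. The count sentence does not remove it, because the sentence that states the feasibility definition leaves the content out.

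**The whole ten-day food log is not the endpoint.** Section 2.1 sets the broad aim of learning whether "CGM paired with technology-driven health behavior data collection is a feasible and acceptable approach to T2D screening", and 3.1 has no scope limit. A reader might therefore compare 32 replies with all prompts sent, about 3 × 10 × 40 = 1,200, and infer that the criterion can pass with nearly all of its data missing. That denominator does not fit. The abstract, 7.1 and 7.4.1 tie the outcome to the challenge or to the challenge days, and the sentence in 2.1 is an overall aim. An unanswered prompt may also be covered by a paper log.

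**The time is what the glucose comparison needs.** The drink is supplied by the study in a known amount, and the two-hour comparison in H2 depends on the logged time. This stands for the glucose challenge, and it is a reason to keep the time criterion under a name that says what it measures. It does not cover the mixed-meal day, which 7.4.1 includes.

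**Later analyses are exploratory.** The prior-day carbohydrate subgroups belong to correlations described as further exploration, and no passage makes them conditional on the logging result. This stands and limits the harm to the primary logging conclusion.

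**Conclusion.** The point holds as a contradiction over what decides a primary criterion. Under the feasibility sentence and 6.2, 32 glucose-drink times among 40 participants are enough to declare logging feasible with no food content recorded. Under the count sentence the same data give zero successes. This follows from the wording and from 0.80 × 40 = 32, and needs no assumption about reply rates.

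How often the two readings would disagree does depend on assumptions. With a challenge time logged by 90% of participants and food content present for 75% of those, the pass probabilities are 0.985 without content and 0.060 with it.

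The change should be made because one primary conclusion rests on it and the correction is cheap. It does not affect the CGM-completeness criterion, H2 or the sample size.

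**What to change.** In 6.2, the synopsis and H1b, replace the single rule with two criteria. Each keeps the plan's 80% bar and uses all enrolled participants as denominator.

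1. **Challenge time documentation:** date and time of the glucose challenge recorded.
2. **Nutrition logging:** mixed-meal entry recorded with date, time, food item, amount, carbohydrate, fat and protein, as 5.3.3 requests.

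Count text and paper logs alike. Draw a conclusion on logging quality only from the second criterion. Report the food-survey response on the challenge days, and on the day before the glucose challenge, descriptively and without a pass bar.

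The cost is a wording change in three places and a tabulation of fields already requested, with no added visits or participant burden. If data are already in, both counts can be reported beside the present one. The downside is that the logging figure may be less favourable. With all 40 in the denominator, if 8 record nothing (20%, as in 7.5), each of the other 32 would need a complete entry to reach the bar.
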